2.5.2.2 PROGRESSION FREE SURVIVAL

The 6 months progression-free survival rate will be estimated and plotted using the Kaplan-Meier product-limit method, along with their corresponding log-log transformed 95% confidence intervals.

2.5.2.2.1 Progression free survival ITT POPULATION

In the ITT population (n=XX), at 6 months the proportion of patients that survived without PD or death was XXXX with a CI95% XXXX-XXXX. The overall median of PFS was XXX months (CI95% XXX-XXX).

Table 180. Progression free survival at 6 and 12 months (ITT)

	N events	Patients at risk	% estimated cumulative survival ratio ¹	95% CI	% of PFS
at 6 months	Cohort 1				
	Cohort 2				
	Cohort 3				
	Cohort 4				
	Cohort 5				
	Cohort 6				
at 12 months	Cohort 1				
	Cohort 2				
	Cohort 3				
	Cohort 4				
	Cohort 5				
	Cohort 6				
Estimated PFS ¹	N	N (%) events	Median (months)	Standard error	95% CI
	Cohort 1				
	Cohort 2				
	Cohort 3				
	Cohort 4				
	Cohort 5				
	Cohort 6				

1: Estimated using Kaplan-Meier product-limit method

[figure not shown]
Table 181. Progression free survival events at 6 months (ITT)

	PFS event	N (%, CI95%)
Cohort 1	Without PD/Death	
	PD	
	Death (without previous PD)	
Cohort 2	Total	
	Without PD/Death	
	PD	
Cohort 3	Death (without previous PD)	
	Total	
	Without PD/Death	
	PD	
	Death (without previous PD)	
	Total	

Sponsor: Grupo Español de Tumores Neuroendocrinos y Endocrinos (GETNE)

	PFS event	N (% , CI95%)
Cohort 4	Without PD/Death	
	PD	
	Death (without previous PD)	
Cohort 5	Total	
	Without PD/Death	
	PD	
Cohort 6	Death (without previous PD)	
	Total	
	Without PD/Death	
	PD	
	Death (without previous PD)	
	Total	

Figure 1 Kaplan Meier curve: PFS (ITT)

Sponsor: Grupo Español de Tumores Neuroendocrinos y Endocrinos (GETNE)

2.5.2.2.2 Progression free survival PP POPULATION

In the PP population (n=XX), at 6 months the proportion of patients that survived without PD or death was XXXX with a CI95% XXXX-XXXX. The overall median of PFS was XXX months (CI95% XXX-XXX).

Table 182. Progression free survival at 6 and 12 months (PP)

	N events	Patients at risk	% estimated cumulative survival ratio ¹	95% CI	% of PFS
at 6 months	Cohort 1				
	Cohort 2				
	Cohort 3				
	Cohort 4				
	Cohort 5				
	Cohort 6				
at 12 months	Total				
	Cohort 1				
	Cohort 2				
	Cohort 3				
	Cohort 4				
	Cohort 5				
Estimated PFS ¹	Cohort 6				
	Total				
	N	N (%) events	Median (months)	Standard error	95% CI
	Cohort 1				
	Cohort 2				
	Cohort 3				
Estimated PFS ¹	Cohort 4				
	Cohort 5				
	Cohort 6				
	Total				

1: Estimated using Kaplan-Meier product-limit method

[figure not shown]
Table 183. Progression free survival events at 6 months (PP)

	PFS event	N (%), CI95%
Cohort 1	Without PD/Death	
	PD	
	Death (without previous PD)	
Cohort 2	Total	
	Without PD/Death	
	PD	
Cohort 3	Death (without previous PD)	
	Total	
	Without PD/Death	
Cohort 4	PD	
	Death (without previous PD)	
	Total	
Cohort 4	Without PD/Death	
	PD	
	Death (without previous PD)	
Cohort 4	Total	

Sponsor: Grupo Español de Tumores Neuroendocrinos y Endocrinos (GETNE)

	PFS event	N (% , CI95%)
Cohort 5	Without PD/Death	
	PD	
	Death (without previous PD)	
	Total	
Cohort 6	Without PD/Death	
	PD	
	Death (without previous PD)	
	Total	
Total	Without PD/Death	
	PD	
	Death (without previous PD)	
	Total	

Figure 2 Kaplan Meier curve: PFS (PP)

Sponsor: Grupo Español de Tumores Neuroendocrinos y Endocrinos (GETNE)

2.5.2.3 OVERALL SURVIVAL

The overall survival rate will be estimated and plotted using the Kaplan-Meier product-limit method, along with their corresponding log-log transformed 95% confidence intervals.

2.5.2.3.1 OVERALL survival ITT POPULATION

In the ITT population (n=XX), at 6 months the proportion of patients that survived was XXXX with a CI95% XXXX-XXXX. The overall median of OS was XXX months (CI95% XXX-XXX).

Table 184. Overall survival at 6 and 12 months (ITT)

	N events	Patients at risk	% estimated cumulative survival ratio ¹	95% CI	% of OS
at 6 months	Cohort 1				
	Cohort 2				
	Cohort 3				
	Cohort 4				
	Cohort 5				
	Cohort 6				
at 12 months	Total				
	Cohort 1				
	Cohort 2				
	Cohort 3				
	Cohort 4				
	Cohort 5				
Estimated OS ¹	Cohort 6				
	Total				
	N	N (%) death	Median (months)	Standard error	95% CI
Estimated OS ¹	Cohort 1				
	Cohort 2				
	Cohort 3				
	Cohort 4				
	Cohort 5				
	Cohort 6				
Estimated OS ¹	Total				

1: Estimated using Kaplan-Meier product-limit method

[figure not shown]
Table 185. Overall survival events at 6 months (ITT)

	OS event	N (%, CI95%)
Cohort 1	No death at end of follow-up	
	Death	
	Total	
Cohort 2	No death at end of follow-up	
	Death	
	Total	
Cohort 3	No death at end of follow-up	
	Death	
	Total	

Sponsor: Grupo Español de Tumores Neuroendocrinos y Endocrinos (GETNE)

	No death at end of follow-up
Cohort 4	Death
	Total
	No death at end of follow-up
Cohort 5	Death
	Total
	No death at end of follow-up
Cohort 6	Death
	Total
	No death at end of follow-up
Total	Death
	Total
	No death at end of follow-up

Figure 3 Kaplan Meier curve: OS (ITT)

Sponsor: Grupo Español de Tumores Neuroendocrinos y Endocrinos (GETNE)

2.5.2.3.2 OVERALL survival PP POPULATION

In the PP population (n=XX), at 6 months the proportion of patients that survived was XXXX with a CI95% XXXX-XXXX. The overall median of OS was XXX months (CI95% XXX-XXX).

Table 186. Overall survival at 6 and 12 months (PP)

	N events	Patients at risk	% estimated cumulative survival ratio ¹	95% CI	% of OS
at 6 months	Cohort 1				
	Cohort 2				
	Cohort 3				
	Cohort 4				
	Cohort 5				
	Total				
at 12 months	Cohort 1				
	Cohort 2				
	Cohort 3				
	Cohort 4				
	Cohort 5				
	Total				
	N	N (%) death	Median (months)	Standard error	95% CI
Estimated OS ¹	Cohort 1				
	Cohort 2				
	Cohort 3				
	Cohort 4				
	Cohort 5				
	Total				

[figure not shown]
1: Estimated using Kaplan-Meier product-limit method

Table 187. Overall survival events at 6 months (PP)

	OS event	N (%, CI95%)
Cohort 1	No death at end of follow-up	
	Death	
	Total	
Cohort 2	No death at end of follow-up	
	Death	
	Total	
Cohort 3	No death at end of follow-up	
	Death	
	Total	
Cohort 4	No death at end of follow-up	
	Death	
	Total	
Cohort 5	No death at end of follow-up	
	Death	
	Total	
Cohort 6	No death at end of follow-up	
	Death	
	Total	

Sponsor: Grupo Español de Tumores Neuroendocrinos y Endocrinos (GETNE)

Total	No death at end of follow-up		
	Death		
	Total		

Figure 4 Kaplan Meier curve: OS (PP)

2.5.2.4 FOLLOW UP

Mean and median for the global follow up are shown below.

Table 188. Follow up: mean and median ITT

	N	Mean, SD (CI95%)	Median (CI95%) [Range]
Follow up			

Table 189. Follow up: mean and median PP

	N	Mean, SD (CI95%)	Median (CI95%) [Range]
Follow up			

Sponsor: Grupo Español de Tumores Neuroendocrinos y Endocrinos (GETNE)

2.6. SAFETY ANALYSIS

The **safety analysis set** will be used in this section and it is defined as: Any patient included in the study receiving at least a single dose of study medication will be evaluable for the toxicity analysis.

Safety profile of cabozantinib and atezolizumab: The number of patients with AEs and SAEs, changes in laboratory values, vital signs, ECGs, and results of physician examinations graded according to the CTCAE v 5.0. This will be analysed using descriptive statistics techniques such as frequency and contingency tables. The final statistical analysis of this endpoint is expected to be performed within 6 months after database closure, which is expected at 12 months after last patient inclusion. However, interim analysis may be performed when analysing other primary endpoints.

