If atezolizumab is temporarily or definitively interrupted for its toxicity, cabozantinib will be continued, unless the toxicity of atezolizumab prevents the administration of cabozantinib or increase the risk of cabozantinib toxicity. In this case, both treatments will be interrupted until toxicity resolution (or NCI CTCAE grade 1) or definitively.

If one of the two drugs is discontinued or interrupted due to toxicity, the administration of the other drug should continue according to the protocol schedule.

All dose reductions and interruptions (including any missed doses), and the reasons for the reductions/interruptions are to be recorded in the eCRF and patient record. An occurrence of autoimmune disease will be declared in this study as a serious adverse event (SAE) at any time during atezolizumab treatment and at any time after the treatment has been stopped.

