7.2.3. Atezolizumab Special warnings and precautions for use

In order to improve the traceability of biological medicinal products, the trade name and the batch number of the administered product should be clearly recorded (or stated) in the patient file.

Most immune-mediated adverse reactions that occurs during treatment with atezolizumab are reversible with the interruptions of atezolizumab and initiation of corticosteroids and/or supportive care. Immune-mediated adverse reactions affecting more than one body system have been observed. Immune-mediated adverse reactions with atezolizumab may occur after the last dose of atezolizumab.

For suspected immune-mediated adverse reactions, thorough evaluation to confirm aetiology or exclude other causes should be performed. Based on the severity of the adverse reaction, atezolizumab should be withheld and corticosteroids administered. Upon improvement to Grade ≤ 1 , corticosteroid should be tapered over ≥ 1 month. Based on limited data from clinical studies in patients whose immune-mediated adverse reactions could not be controlled with systemic corticosteroid use, the administration of other systemic immunosuppressants may be considered.

Atezolizumab must be permanently discontinued for any Grade 3 immune-mediated adverse reaction that recurs and for any Grade 4 immune-mediated adverse reactions, except for endocrinopathies that are controlled with replacement hormones.

1) Pulmonary events

Cases of pulmonary events, including dyspnea, cough, fatigue, pulmonary infiltrates and pneumonitis, have been observed in clinical trials with atezolizumab. Patients should be monitored for pulmonary signs and symptoms.

2) Hepatic events

Immune-mediated hepatitis has been associated with the administration of atezolizumab. Patients eligible for study treatment must have adequate liver function, as manifested by measurements of total bilirubin and hepatic transaminases; liver function will be monitored throughout study treatment. Management guidelines for hepatic events are provided in Appendix 1.

3) Gastrointestinal events

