9.2.1.1. Adverse Event (AE)

An AE is any untoward medical occurrence in a patient or clinical investigation subject administered a medicinal product and that does not necessarily have a causal relationship with this treatment. An AE can therefore be the development of a new medical condition, or the deterioration of a pre-existing medical condition. This includes any unfavorable and unintended sign (e.g. tachycardia, enlarged liver), symptom (e.g. nausea, chest pain) or the abnormal results of an investigation (e.g. laboratory findings, electrocardiogram) temporally associated with the use of a medicinal product, whether or not considered related.

This requirement includes specific events or symptoms associated with cancer progression or general clinical deterioration to ensure potential toxicities are not overlooked. Radiographic progression without associated clinical sequelae is not considered an AE; terms such as 'disease progression' should be avoided. Pre-existing medical conditions that worsen during a study will be recorded as AEs. Abnormal laboratory values, ECG findings, or vital signs are to be recorded as AEs if they meet the criteria described in Section 9.3.

All untoward events that occur after informed consent through 30 days (100 days for SAEs and AESIs) after the date of the decision to permanently discontinue study treatment (defined as the later of the date of the decision to discontinue all study treatment or the date of the last dose of any study treatment) are to be recorded by the investigational site.

At each scheduled and unscheduled visit, AEs are to be identified and assessed based upon study procedures, routine and symptom-directed clinical investigations, and subject query/report.

Assessment of the relationship of the AEs to study treatment by the investigator will be based on the following two definitions:

- Not Related: An event is assessed as not related to study treatment if it is attributable to another cause and/or there is no evidence to support a causal relationship.
- Related: An event is assessed as related to study treatment when there is a reasonable possibility that study treatment caused the event. Reasonable possibility means there is evidence to suggest a causal

relationship between study treatment and the event. This event is called a suspected adverse reaction. A suspected adverse reaction implies a lesser degree of certainty about causality than adverse reaction, which means any AE caused by a drug.

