9.3.2. SAE Reporting

As soon as an investigator becomes aware of an AE that meets the criteria for an SAE, the investigator will document the SAE to the extent that information is available.

SAEs, regardless of causal relationship, must be reported to the Sponsor or designee within 24 hours of the investigator's knowledge of the event by submitting the completed SAE report form and any other pertinent SAE information as indicated on the SAE Reporting form (or in the SAE Reporting form Completion Guidelines) and confirming the report was received. Forms for reporting SAEs and contact information will be provided to the study sites.

Reporting Information for safety reports

To report initial or follow-up information to Ipsen/Roche, a completed Clinical Study Serious Adverse Event (SAE) report form should be sent to the following within 24 hours of becoming aware of the event:
 
Serious Adverse Events
 
All serious adverse events must be reported by fax within 24 h to MFAR Clinical Research, S.L.
 
by fax ([name]) or e-mail to [contact]

SAEs that must be recorded on an SAE Reporting form include the following:

- All SAEs that occur after informed consent and through 100 days after the date of the decision to permanently discontinue study treatment (ie, the later of the date of the decision of the investigator to permanently discontinue study treatment or the date of the last dose of any study treatment taken by the subject) or the date the subject is deemed to be a screen failure.
- Any SAEs assessed as related to study treatment or study procedures, even if the SAE occurs more than 100 days after the date of the decision to permanently discontinue study treatment.

Note: If the subject does not meet the eligibility criteria during screening, then SAEs only need to be reported from the time the subject signs the informed consent until the day when the subject has been determined to not be eligible for study participation.

SAEs that occur after the initiation of study treatment through 100 days after the date of the decision to permanently discontinue of study treatment must also be recorded on the CRF page.

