9.4. ADVERSE EVENTS OF SPECIAL INTEREST

Adverse events of special interest (AESIs) consist of immune-mediated AEs associated with ICIs, cases of potential DILI, and suspected transmission of an infectious agent by the study treatment (Table 3).

AESIs will be reported to the Sponsor or designee using the SAE reporting form irrespective of whether the event is serious or nonserious; all AESIs must be reported within 24 hours using the SAE process as described in Section 9.3.

Guidance for management of immune-mediated AEs associated is provided in Investigator's Brochure for atezolizumab.

Table 3. Adverse Events of Special Interest

Category	Event
DILI	
Cases of potential Drug-induced Liver Injury (DILI) that include an elevated ALT or AST in combination with either an elevated bilirubin or clinical jaundice, as defined by Hy's Law and based on the following observations:
Treatment-emergent ALT or AST $> 3 \times$ baseline value in combination with total bilirubin $> 2 \times$ ULN (of which $\geq 35\%$ is direct bilirubin).Treatment-emergent ALT or AST $> 3 \times$ baseline value in combination with clinical jaundice.
Other	
Suspected transmission of an infectious agent by the study treatment, as defined below:
Any organism, virus, or infectious particle (eg, prion protein transmitting transmissible spongiform encephalopathy), pathogenic or non-pathogenic, is considered an infectious agent. A transmission of an infectious agent may be suspected from clinical symptoms or laboratory findings that indicate an infection in a patient exposed to a medicinal product. This term applies only when a contamination of study treatment is suspected.
irAE	
Systemic lupus erythematosus
irAE	
Events suggestive of hypersensitivity, infusion-related reactions, cytokine release syndrome, HLH and MAS
irAE	
Nephritis
irAE	
Ocular toxicities (eg, uveitis, retinitis)
irAE	
\geq Grade 2 cardiac disorders (eg, atrial fibrillation, myocarditis, pericarditis)
irAE	
Vasculitis
irAE	
Autoimmune hemolytic anemia

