9.5. FOLLOW-UP OF ADVERSE EVENTS

Non-serious AEs are to be recorded in the CRF until 30 days after the date of the decision to discontinue study treatment (the later of the date of the decision by the investigator to permanently discontinue study treatment or the date of the last dose of any study treatment taken by the subject). The status of unrelated SAEs that are ongoing after the date of the decision to discontinue study treatment will be documented as of the 100-day FU-2 visit.

All AESIs (regardless of seriousness) and all related SAEs that are ongoing 100 days after the date of the decision to discontinue study treatment (the later of the date of the decision by the investigator to permanently discontinue study treatment or the date of the last dose of any study treatment taken by the subject), and AEs assessed as related that led to study treatment discontinuation that are ongoing 100 days after the date of the decision to discontinue study treatment, are to be followed until either:

- the AE has resolved
- the AE has improved to Grade 2 or lower
- The Investigator determines that the event has become stable or irreversible.

Further details on follow-up procedures are summarized in section 8.1 study determinations chart.

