1.5. SUMMARY OF STUDY DATA

For each categorical variable, the results will be summarised by frequencies and percentages. For each continuous variable, the results will be summarised by descriptive statistics such as median, range, and interquartile range or by means, standard deviations, and 95 % confidence intervals (CIs). For proportions, point estimates and exact 95 % confidence intervals will be calculated. For time to event endpoints, Kaplan-Meier estimates at selected time points and corresponding curves will be presented. Time to event is derived relative to the first study treatment administration. Laboratory values will be expressed as absolute values and in grades (ordinal categorical variables) according to NCI CTCAE v 5.0.

Treatment-emergent AE (AEs starting after the administration of study treatment and up to study completion) will be summarised by system organ class and preferred term. Grading will be presented by type and in tables showing the frequency and percentage of the within-patient worst grades. In addition, grade ≥ 3 AEs will be summarised separately. Full analysis details will be outlined in the statistical analysis plan (SAP).

Sponsor: Grupo Español de Tumores Neuroendocrinos y Endocrinos (GETNE)

Continuous data will be presented with the number of observations, mean value, standard deviation, minimum, maximum, and median. Categorical data will be presented as counts and percentages. Individual subject data will be listed.

Vital signs, ECG parameters, clinical laboratory data (haematology, serum biochemistry, and urinalysis) will be presented in tabular form. Values outside the reference range will be flagged, and the clinically significantly abnormal values will be listed in tabular form. Adverse events will be tabulated by system organ class and preferred term after medical coding using the according to NCI CTCAE v 5.0.

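### Protocol 9.5 closes the CRF to non-serious AEs at day 30 without excepting AESIs, although 9.2.1.1 has AESIs recorded to day 100, so late non-serious AESIs can miss the planned safety counts

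*Combined protocol and SAP*

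**What the plan says.** The safety endpoint in protocol 10.2.2 and SAP 2.6 is "The number of patients with AEs and SAEs, changes in laboratory values, vital signs, ECGs, and results of physician examinations". SAP Tables 190 and 206 (numbering as in the SAP body) turn this into patient counts, overall and per cohort, with separate rows for any AE, AEs related to each drug, and SAEs.

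Four places decide which events can enter those counts after treatment ends:

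- Protocol 9.2.1.1 sets the collection period: "All untoward events that occur after informed consent through 30 days (100 days for SAEs and AESIs) after the date of the decision" to stop treatment for good.
- Protocol 9.5 sets the CRF period for non-serious events: "Non-serious AEs are to be recorded in the CRF until 30 days after the date of the decision to discontinue study treatment". The clock starts at the later of the investigator's decision and the last dose.
- Protocol 9.3.2 (SAE Reporting) says that SAEs up to 100 days after the decision to "permanently discontinue of study treatment must also be recorded on the CRF page". It does not mention AESIs.
- SAP 1.5, like protocol 10.6, defines treatment-emergent events as "AEs starting after the administration of study treatment and up to study completion".

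The reporting route for AESIs is in protocol 9.4: "AESIs will be reported to the Sponsor or designee using the SAE reporting form irrespective of whether the event is serious or nonserious".

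**The concern.** The protocol asks for AESIs to day 100 because it expects late ones. Section 7.2.3 warns: "Immune-mediated adverse reactions with atezolizumab may occur after the last dose of atezolizumab". Yet the sentence that governs the CRF for non-serious events stops at day 30, and the only explicit instruction to use the CRF to day 100 is written for SAEs. A non-serious AESI with onset between those days therefore has a reporting route but no stated place in the CRF.

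If sites follow 9.5 as written, such events are absent from the AE and atezolizumab-related counts, and those counts are biased downwards. The SAP does not warn the reader. Its window runs to study completion, so the tables would appear to cover a period in which non-serious events were not being entered.

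**Working it through.** **Step 1. The rules side by side.**

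| Place | Events | Window after treatment | Record |
|---|---|---|---|
| 9.2.1.1 | SAEs and AESIs | to day 100 | recorded by the site, no form named |
| 9.2.1.1 | all other events | to day 30 | as above |
| 9.3.2 | SAEs | to day 100 | SAE form and CRF |
| 9.3.2 | SAEs related to treatment or procedures | no upper limit | SAE form |
| 9.4 | AESIs, serious or not | report within 24 hours | SAE form |
| 9.5 | non-serious AEs | to day 30 | CRF |
| SAP 1.5, protocol 10.6 | treatment-emergent AEs | to study completion | counted in tables |

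**Step 2. Follow one event.** Take a non-serious AESI starting on day 60. Under 9.2.1.1 it must be recorded. Under 9.4 it goes to the sponsor on the SAE form. The CRF sentence in 9.3.2 does not reach it because it is not an SAE, and 9.5 does not reach it because it is non-serious and after day 30. It lies inside the SAP 1.5 window and should be counted. If the tables are built from the CRF, it is in neither the AE row nor, being non-serious, the SAE row. That the tables come from the CRF is an assumption: protocol section 14 puts trial data in the EDC system, and the SAP annex on database management is still a placeholder.

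**Step 3. Length of the gap.** 100 − 30 = 70 of the 100 post-treatment AESI days fall outside the non-serious CRF period. This is calendar time, not a share of events. Protocol 9.4.1 says most immune-related events arise in the first 12 weeks of exposure, so the share of events is smaller.

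**Step 4. What one patient is worth.** The tables count patients, so a row changes only if the patient has no other event in it. The change is then 100/n percentage points. The denominators come from the synopsis: 9 or 24 per cohort, and 6 × 9 = 54 to 6 × 24 = 144 overall.

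| n | Points per patient |
|---|---|
| 9 | 100/9 = 11.1 |
| 24 | 100/24 = 4.2 |
| 54 | 100/54 = 1.9 |
| 144 | 100/144 = 0.7 |

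**Step 5. Which rows are exposed.** The any-AE row will hardly move: section 7.1.3 cites diarrhoea in 63%, palmar-plantar erythrodysesthesia in 44% and hypertension in 36% of cabozantinib-treated patients. The exposed rows are those for atezolizumab-related events and for individual terms.

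**Step 6. What cannot be computed.** The documents give no AESI rate, no split by seriousness and no expected time on treatment. An expected number of lost events would be assumption throughout, so none is offered.

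**The case against.** The strongest reply is that the sections can be read together. Section 9.2.1.1 makes AESIs an express exception to the 30-day rule. Section 9.4 sends every AESI through the process of section 9.3, which for SAEs includes CRF entry to day 100. Section 9.5 itself treats AESIs separately when it covers events still ongoing at day 100. The opening of section 9 asks for all adverse events in the eCRF, and 8.2.2 and 8.2.3 speak of recording during follow-up. A careful site could conclude that late non-serious AESIs belong in the CRF.

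That reading is plausible, and it rules out saying that these events will certainly be lost. It does not close the gap, because no sentence says it for non-serious AESIs. The eCRF instruction in section 9 is tied to Table 2, whose AE/SAE/AESI row ends at the end-of-treatment visit. That row is also blank at screening, where events are nevertheless collected, so it does not settle the window by itself. Section 9.5 mentions a 100-day follow-up visit, but neither schedule table contains one.

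The objection that few events are affected also stands. Infusion reactions occur within 24 hours of dosing (7.2.3), so they cannot start on days 31 to 100, and several other Table 3 entries would usually meet a seriousness criterion.

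A reader might also infer a second conflict: 7.2.2 declares any autoimmune disease an SAE, while 9.4 allows AESIs to be non-serious. The documents do not require that reading. Section 7.2.2 is a specific declaration. The wording in 9.4 covers the whole AESI list, and 9.3.1 admits SAE status on medical judgement. Keeping 7.2.2 also narrows the gap, because an autoimmune disease that is an SAE falls under the day-100 CRF rule.

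**Conclusion.** The window mismatch is real, and the SAP does not resolve it. Taken literally, 9.5 leaves non-serious AESIs with onset on days 31 to 100 out of the CRF, and so out of the AE and atezolizumab-related counts. This rests on two assumptions: that the safety tables are drawn from the CRF, and that at least some sites apply 9.5 as written.

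The direction is downward. The size is probably small and cannot be quantified from the documents; the per-patient shifts show only how sensitive a row is. The ORR analysis, its error rates and the sample size are not involved.

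A reader might go further and infer that the six cohorts would be counted unequally. That does not follow: sites are not cohorts (SAP Table 5 crosses the two), and protocol 5.1 applies the same assessments to every cohort. The severity is minor.

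**What to change.** 1. **Protocol 9.5:** add one sentence that AESIs of any seriousness with onset up to day 100 are entered on the CRF AE page.
2. **Before database closure:** reconcile AESI reports received on the SAE form with the CRF, so that events already reported for patients off treatment are recovered.
3. **SAP 1.5, and the matching sentence in protocol 10.6:** replace the window to study completion with the collection windows, namely AEs to 30 days, SAEs and AESIs to 100 days, and related SAEs at any later time. A plain 100-day cap on SAEs would be wrong, because 9.3.2 requires later related SAEs to be reported.
4. **Autoimmune disease:** keep it as an SAE under 7.2.2, with at most a footnote marking cases that are serious only by that declaration. Limiting the SAE rows to events meeting 9.3.1 would make the SAP override the protocol.

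The cost is a sentence in 9.5, a wording change for the analysis window, a little extra data entry and one reconciliation. No new visits or tables are needed. The reconciliation assumes that AESIs can be identified on the SAE form, which is not among the documents. Events never asked about after the end-of-treatment visit will stay missing.
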